Continuous Glucose Monitoring in Hospitalized Patients With Diabetes Mellitus

NCT#04653454

12August2020

IRB Minimal Risk Protocol Template

Note: If this study establishes a human specimen repository (biobank) for research purposes, do not use this template. Use the Mayo Clinic Human Specimen Repository Protocol Template found on the IRB home page under Forms and Procedures at

[REDACTED]

First-time Use: Use this template to describe your study for a new IRB submission.

1. Complete the questions that apply to your study.
2. Save an electronic copy of this protocol for future revisions.
3. When completing your IRBe application, you will be asked to upload this document to the protocol section.

Modification: To modify this document after your study has been approved:

1. Open your study in IRBe. Click on the study 'Documents' tab and select the most recent version of the protocol. Save it to your files.
2. Open the saved document and activate "Track Changes".
3. Revise the protocol template to reflect the modification points, save the template to your files
4. Create an IRBe Modification for the study and upload the revised protocol template.

General Study Information

Principal Investigator: [name].

Study Title: CGM use in hospitalized patients with diabetes mellitus.

Protocol version number and date: Version 1.0, 8/12/2020

Research Question and Aims

Hypothesis: Patient's own CGM (continuous glucose monitor) used in the hospital will be as accurate as POC (point of care) glucose monitors and acknowledgement by providers of high and low glucose trends will prevent episodes of hyper and hypoglycemia.

Aims, purpose, or objectives:

1. To determine if patient's own CGMs worn in the non-ICU hospital setting have adequate accuracy for blood glucose monitoring when compared to point-of-care capillary glucose measurement.
2. To determine if alerts given by CGMs worn in the non-ICU hospital would prevent episodes of hyperglycemia and hypoglycemia.

Background (*Include relevant experience, gaps in current knowledge, preliminary data, etc.*):

Diabetes Mellitus (DM) affects approximately 34.2 million (10.5%) Americans. Hyperglycemia and hypoglycemia in hospitalized patients have been associated with unfavorable clinical outcomes, including higher rates of sepsis, deconditioning, mortality and longer hospital stay. Untreated

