The study will use data that have been collected under another IRB protocol. Include in the Methods section and enter the IRB number from which the research material will be obtained. *When appropriate, note when subjects have provided consent for future use of their data and/or specimens as described in this protocol.*

Enter one IRB number per line, add more lines as needed

Data Specimens Data & Specimens _____

Data Specimens Data & Specimens _____

Data Specimens Data & Specimens _____

Data Analysis

Power analyses may not be appropriate if this is a feasibility or pilot study, but end-point analysis plans are always appropriate even if only exploratory. Provide all information requested below, or provide justification if not including all of the information.

Power Statement:

Data Analysis Plan:

Data will be described as percentages or means. Pearson χ^2 and Kruskal Wallis tests will be used to compare categorical and continuous variables respectively. Odds ratios, 95% confidence intervals and p-values will be reported for each model. All tests of significance will be 2-sided and the level of statistical significance will be set at p-value < 0.05.

Mean Absolute Relative Differences will be calculated between matched pairs of POC monitors and the closest CGM reading (within 5 minutes of POC). Additionally, level of agreement between the two devices will be examined with Bland-Altman plots, with particular attention focused on detection agreement in range (70-180 g/dl). Poisson or negative binomial regression will be utilized to assess count variables such as number of alarms, nurse notification, and hypo or hyperglycemia events adjusting for patient characteristics. Finally, longitudinal analysis will be conducted to determine differences associated with medications, clinical parameters or diagnosis. Analysis will seek to define if there are any differences between CGM and POC measurement based on these changes.

Endpoints

Primary: CGM accuracy - mean absolute relative difference (MARD)

Secondary:

- CGM accuracy at detection of hypo or hyperglycemia episodes when compared with POC monitors. (MARD for readings <70g/dl, >180g/dl, >250g/dl)
- CGM accuracy for detecting time in range (70-180 g/dl MARD).
- Number of CGM alarms and the clinical result of these alarms: nurse notification, treatment of hypo or hyperglycemia episodes, treatment for rapid declining glucose alarms.

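### Every endpoint headed CGM accuracy is a mean relative error, so none reports how often CGM is badly wrong or misses a low or a high

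*Combined protocol and SAP*

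**What the plan says.** Aim 1, under Research Question and Aims, asks whether patients' own CGMs "have adequate accuracy for blood glucose monitoring when compared to point-of-care capillary glucose measurement". No numerical meaning of adequate is given.

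The Endpoints section answers with averages:

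- Primary: "Primary: CGM accuracy - mean absolute relative difference (MARD".
- Secondary, accuracy at detecting hypo- or hyperglycemia: "MARD for readings <70g/dl, >180g/dl, >250g/dl".
- Secondary, in range: "CGM accuracy for detecting time in range (70-180 g/dl MARD".

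The Data Analysis Plan computes MARD from "matched pairs of POC monitors and the closest CGM reading (within 5 minutes of POC" minutes rule, that is, the nearest CGM value inside that window. It adds that the "level of agreement between the two devices will be examined with Bland-Altman plots", "with particular attention focused on detection agreement in range (70-180 g/dl". It also plans a longitudinal analysis of whether CGM-POC differences vary with medications, clinical parameters or diagnosis.

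Nothing in the plan reports the share of pairs inside or outside an error limit, a percentile of the error, an error grid, or sensitivity and specificity for low or high glucose. The documents print the glucose unit as g/dl; I read it as mg/dl.

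**The concern.** Whether CGM is adequate for monitoring turns largely on how often a reading is far from POC, and on how often a low or high is missed. A mean answers neither question. If most sensors read well and a minority read far off, the mean can look the same as when all sensors carry moderate error. The protocol itself looks for medications, clinical parameters and diagnoses that disturb readings, so it expects that some patients may read worse than others.

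The detection endpoint has a further problem. A mean error among readings below 70 does not say how many POC lows the CGM also showed as low. The relative scale also weighs the same absolute error differently: 10 mg/dl is 10/60 = 17% at 60 but 10/200 = 5% at 200.

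At stake is the Aim 1 conclusion, which could be drawn from MARD with no reported rate of large errors or missed events beside it.

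**Working it through.** The documents give no expected MARD, error SD, error distribution or error limit, so there is no stated figure to reproduce. The check asks whether a fixed MARD fixes the rate of large errors. **All inputs below are assumed, for illustration.**

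**Device A, normal relative error, MARD 10%.** For a zero-mean normal error, MARD = SD × sqrt(2/pi) = 0.798 × SD, so SD = 10/0.798 = 12.53%. The share beyond T is 2 × (1 − Phi(T/SD)).

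**Device B, same MARD, 90/10 mixture of two normals.** Require 0.798 × (0.9 s1 + 0.1 s2) = 10, so s2 = 125.33 − 9 s1.

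- s1 = 7.5 gives s2 = 57.8.
- s1 = 9 gives s2 = 44.3.

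The share beyond T is 0.9 × 2(1 − Phi(T/s1)) + 0.1 × 2(1 − Phi(T/s2)).

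| Beyond | A | B, s1 = 9 | B, s1 = 7.5 | Ratio B/A |
|---|---|---|---|---|
| 15% | 23.1% | 16.0% | 12.0% | 0.5-0.7 |
| 20% | 11.1% | 8.9% | 8.0% | 0.7-0.8 |
| 30% | 1.7% | 5.1% | 6.0% | 3.0-3.6 |
| 40% | 0.14% | 3.7% | 4.9% | 26-35 |
| 50% | 0.007% | 2.6% | 3.9% | about 390-585 |

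Per 1,000 pairs, about 1 reading against 37 to 49 is off by more than 40%.

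**Dependence on MARD.** Multiply all SDs by 1.5, so that MARD is 15%. Beyond 40%, A has 3.3% and B 5.7-6.5%, a ratio of about 2. Multiply by 2, so that MARD is 20%, and the ratio at 40% is 0.7-0.8.

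**What Bland-Altman limits would show at MARD 10%, on the relative scale.**

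- A: 1.96 × 12.53 = ±24.6%.
- B, s1 = 9: SD = sqrt(0.9 × 9² + 0.1 × 44.3²) = 16.4, limits ±32.2%.
- B, s1 = 7.5: SD = sqrt(0.9 × 7.5² + 0.1 × 57.8²) = 19.6, limits ±38.5%.

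The limits separate the devices, but they do not give the rate. Read as normal, SD 16.4 implies 1.5% beyond 40%, where the mixture has 3.7%. SD 19.6 implies 12.6% beyond 30%, where the mixture has 6.0%.

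**Limit of the example.** A normal component with SD 44-58% puts 1.2-4.2% of itself below −100%, which is impossible for glucose. That is at most 0.1 × 4.2% = 0.4% of all pairs.

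**The case against.** The strongest reply is that MARD does not stand alone. A reader might infer that accuracy is judged only by an average, or that a harmful tail would go unseen. The documents do not support either reading. Bland-Altman plots are planned; they show every pair and need no normality to do so, and in the example even their limits differ between devices. The longitudinal analysis and the endpoint on interfering factors may pick out groups that read badly, failed sensors are counted, and MARD is split by glucose range, which partly separates the relative-scale effect.

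A reader might also infer that devices with equal MARD differ about 30-fold in large errors. That is one cell of the table, at an assumed MARD and threshold. At 15% and 20% the heavy-tailed device looks better than the normal one.

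Nor do the documents support an inference of direct treatment harm: Study Design and Methods bases treatment decisions on POC readings.

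All of this stands and narrows the point. What remains is that the plots are not an endpoint, carry no acceptance limit, concentrate on 70-180 and produce no rate. The other analyses likewise give no share of large errors and no count of missed lows or highs.

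**Conclusion.** The point holds in a limited form. The primary endpoint and both secondary endpoints headed CGM accuracy are MARDs, so none gives the rate of large errors, and the detection endpoint does not measure detection. This part rests on the text alone. The Bland-Altman plots reduce the gap without closing it.

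The numerical size is an illustration, conditional on an assumed MARD and assumed error shapes. It shows that MARD does not determine the large-error rate in either direction. It does not predict what this study will find, and no single ratio should be quoted from it.

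**What to change.** Keep MARD as the primary endpoint. Add these secondary accuracy endpoints from the same matched pairs:

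- **Large errors.** The share of pairs with CGM within 15, 20, 30 and 40% of POC, using the same numbers in mg/dl at low glucose, with the switch point stated in advance. Add the 95th percentile of the absolute relative difference or an error-grid table. The 30% and 40% limits are needed because 15% and 20% alone can favour the heavy-tailed device.
- **Detection.** Sensitivity and specificity of CGM for POC <70, >180 and >250.
- **Low readings.** Mean absolute difference in mg/dl beside MARD for readings <70.

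Give confidence intervals that allow for repeated readings per patient. State in the plan that the Aim 1 conclusion rests on MARD together with the share of large errors.

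The cost is a few more summaries, with no new data or patients. Sensitivity below 70 may be imprecise if lows are few; the documents give no expected number. The other downside is a figure on which CGM may look less favourable.

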All patients admitted to the hospital in inpatient or observation status and having a CGM monitor attached will be screened and identified by providers and nurses. An order will be placed by providers to continue patient's home CGM monitor use in the hospital. A CGM patient agreement describing the hospital policy for use of CGMs will be provided to the patient for signature. (see attached agreement) Patients will be encouraged to continue to wear their CGMs in the hospital unless their presence interferes with patients' medical care. CGM presence will be recorded by nursing in patient chart under LDA (lines, drains, airway) section. A daily report will be run and these patients identified. Patients will be approached by research staff and asked to be enrolled in the study. A research consent will be reviewed with the patients and will be provided to patients for signature. Patients will be asked to continue to use their home CGMs in the hospital. If the sensor will reach the end of life patients have the option to place a new sensor and follow manufacturer recommendations for calibration and setting. Patients are responsible to provide their own sensors, transmitters, readers during the hospitalization period. If it is determined that the current sensor will interfere with the in-hospital medical and surgical care (MRI testing, procedure at the site, etc.), patient will be asked by their providers to remove the sensor and transmitter. Patients will have the option to replace the sensor after the procedure if they so desire. Patients will continue to monitor their glucose via CGM and their approved devices. For flash sensors, patients will be asked to scan their sensor at least every 8 and as needed. CGMs that require calibration will be calibrated by patients using hospital POC glucose meter readings. .

Patients alerted by their CGM about low glucose levels or fast downward or upward trending will be asked to notify their nursing staff. A POC blood glucose check will be done by nursing staff to confirm the alert or the trend. Treatment decisions will be made based on POC readings.

During hospitalization patients will continue to have their blood glucose checked with POC glucose monitor per hospital policy.

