- Time in therapeutic range for glucose as measured by CGM and POC glucose monitor.
- Detection of medications, clinical parameters or diagnoses that would interfere with CGM reading.
- Effect of CGM use on length of hospital stay, post-surgical duration of hospitalization

Clinical safety measures:

- Number of sensors with failure.
- Number of sensors removed for procedure.
- Number of sensor related skin reaction (contact dermatitis, infection)

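### The secondary endpoints on detecting low glucose, high glucose and time in range are defined only by range-specific MARD, and no planned analysis gives a catch, miss or false-flag rate

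*Combined protocol and SAP*

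**What the plan says.** The Endpoints section names two secondary endpoints in terms of detection and gives each one metric. The entry for low and high readings is "CGM accuracy at detection of hypo or hyperglycemia episodes when compared with POC monitors. (MARD for readings <70g/dl, >180g/dl, >250g/dl"). The separate entry for the in-range band follows the same pattern, with a single MARD in brackets: "CGM accuracy for detecting time in range (70-180 g/dl MARD").

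The outcomes list under Study Design and Methods repeats the first of these without a metric.

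The Data Analysis Plan computes MARD on pairs made of a POC value and the closest CGM value within 5 minutes. It adds Bland-Altman plots, "with particular attention focused on detection agreement in range (70-180 g/dl"), and Poisson or negative binomial regression for counts of alarms, notifications and glucose events.

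Two further secondary endpoints come near the subject: "Time in therapeutic range for glucose as measured by CGM and POC glucose monitor" and "Number of CGM alarms and the clinical result of these alarms: nurse notification", the latter followed by treatment results.

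The Methods also describe what follows an alert. The patient's part is: "Patients alerted by their CGM about low glucose levels or fast downward or upward trending will be asked to notify their nursing staff". The response on the ward is given in the next sentence of that section: "A POC blood glucose check will be done by nursing staff to confirm the alert or the trend". On calibration they say: "CGMs that require calibration will be calibrated by patients using hospital POC glucose meter readings".

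**The concern.** Detection is a classification question: when POC is below 70, is CGM also below 70, and how often does CGM read below 70 when POC does not? MARD discards the sign of the error and takes no account of the cutoff, so it cannot answer either part.

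The plan does not leave the metric open. It names one that does not measure what the endpoint asks. Followed as written, the trial would report an average error per glucose band under the heading of detection, and readers would not learn what share of lows and highs the patient's own sensor caught, missed or falsely flagged. Aim 2 asks whether CGM alerts would prevent such episodes, and the Background justifies the study by episodes that POC testing fails to detect, so these rates are central to its purpose.

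**Working it through.** **1. Two readings.** Take POC = 65. For CGM = 71.5, |71.5 - 65|/65 = 0.10, and the low is missed. For CGM = 58.5, |58.5 - 65|/65 = 0.10, and the low is caught. MARD scores them alike.

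**2. Detection at a fixed MARD.** The plan states no bias, error spread or glucose distribution, so all inputs here are assumed. The model is CGM = POC × (1 + b + sZ), with Z standard normal and b the relative bias. MARD is fixed at 0.0933 by solving for s in

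MARD = s√(2/π)·exp(-b²/2s²) + b[1 - 2Φ(-b/s)].

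This gives s = 0.117 (b = 0), 0.115 (±0.02), 0.110 (±0.04) and 0.080 (±0.08). At a given POC value, P(CGM < c) = Φ((c/POC - 1 - b)/s), which is averaged over the assumed POC range. Paired entries are positive bias / negative bias.

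| Quantity (assumed POC range) | b = 0 | ±2% | ±4% | ±8% |
|---|---|---|---|---|
| Lows <70 caught (54-70) | 82.2% | 78.5 / 85.9 | 74.8 / 89.6 | 66.7 / 97.3 |
| Lows <70 caught (40-70) | 90.5% | 88.5 / 92.4 | 86.5 / 94.4 | 82.2 / 98.6 |
| Falsely flagged <70 (70-100) | 12.8% | 9.9 / 15.6 | 7.1 / 18.4 | 1.7 / 23.7 |
| Highs >180 caught (180-250) | 86.0% | 89.1 / 82.9 | 92.2 / 79.8 | 98.2 / 74.0 |
| Highs >250 caught (250-350) | 86.4% | 89.4 / 83.3 | 92.4 / 80.3 | 98.2 / 74.7 |

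The b = 0 column shows that MARD and mean bias together still do not fix the rate: the same sensor catches 82% or 90% of lows depending on how far below 70 they lie.

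**3. A second model.** Two million simulated pairs used lognormal POC (median 160, log-SD 0.40) and CGM error SD 10%, all assumed. With bias of -10% and +10%, MARD among POC <70 was 11.6% and 11.7%, but 3.9% and 40.8% of lows were missed, and 56% and 10% of the CGM readings below 70 were false.

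**4. The other planned analyses.**

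- *Bland-Altman plots* show signed bias and spread, so they would separate two oppositely biased sensors. The phrase about detection agreement names no statistic and covers only 70-180.
- *Time in range by device* compares totals. Take 100 pairs with each device in range for 70. If 60 pairs are in range on both, 70 - 60 = 10 are in range on CGM only and 10 on POC only. CGM then catches 20/30 = 67% of the POC out-of-range readings and falsely flags 10/70 = 14% of the in-range ones. The same totals also fit 30/30 caught with no false flags.
- *Alarm results* hint at how many alerts were confirmed but say nothing about misses. The Methods name a POC check for low and trend alerts only, not for high-level alerts.
- *Count regression* models numbers of events and does not pair the two devices.

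**5. The banding device.** Pairs are indexed to POC, so POC is the natural choice, but the plan does not say so. Bands set by POC leave out false flags; bands set by CGM leave out misses.

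**The case against.** The strongest reply has four parts.

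- *The plan does mention detection agreement, and the rest is labelling.* The phrase shows intent, but it is attached to Bland-Altman plots in 70-180 and does not reach <70, >180 or >250. Renaming the endpoint as range-specific accuracy would remove the mismatch in words, but the outcomes list states detection without MARD, so detection appears to be what is wanted.
- *The large contrasts come from chosen inputs.* This stands in part. The widest gap needs ±8% bias and lows close to the cutoff. At ±2% with POC on 40-70 it is only 88% against 92%, and Bland-Altman plots would reveal a large bias. The zero-bias result does not rely on bias.
- *Sensitivity has its own weaknesses.* It depends on the spread of POC values, and it counts POC 69 with CGM 71 as a full miss. Both are true, and they are reasons to keep MARD and bias beside it. It is still the quantity the endpoint asks for.
- *Restricting the main estimate to scheduled checks goes too far.* The Background describes standard checks as before meals and at bedtime, so nocturnal lows would be thinly covered. That limit is real and should be stated. Pooling is not neutral, however: checks prompted by a low alert favour pairs where CGM already reads low. If k such pairs, low on both devices, are added per scheduled low, sensitivity S becomes (S + k)/(1 + k), and 0.785 rises to 0.857 at k = 0.5 or 0.892 at k = 1 (k assumed).

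**Conclusion.** The concern holds. Both detection endpoints rest on a metric that cannot separate a caught reading from a missed one, and no other planned analysis supplies the missing rate. That conclusion follows from the definition of MARD and the text of the plan, and needs none of the assumed inputs.

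The size does depend on them. At one MARD of 9.3%, the gap in lows caught between opposite biases runs from about 4 points (±2%, POC 40-70) to about 31 points (±8%, POC 54-70).

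This should be fixed, but it does not threaten the trial. The endpoints are secondary, the primary MARD endpoint is unaffected, and treatment decisions rest on POC.

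**What to change.** **Endpoints and Data Analysis Plan.** For these two endpoints, name POC as the reference and report, from the planned 5-minute pairs, the sensitivity, specificity, PPV and NPV of CGM at <70, >180, >250 and within 70-180, with 95% confidence intervals clustered by patient. State that results are per pair, not per episode, because episodes between POC checks have no reference value. Keep range MARD, banded by POC, and signed bias as supportive measures.

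**Data collection.** Record the reason for each POC check: scheduled, low-glucose alert, trend alert or calibration. Base the main estimate on scheduled checks whose POC value was not entered into the sensor as a calibration for the paired reading. Report low-alert checks separately as the share confirmed below 70 by POC, and do not count trend alerts as flags for <70.

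**Cost.** A few lines of text and one data field, which depends on nursing documentation or later linkage. The cross-tabulations need no new measurements. Few scheduled, non-calibration pairs will lie below 70, so that interval will be wide. With an assumed 50 such pairs and sensitivity of 82%, the half-width is 1.96 × √(0.82 × 0.18/50) = 0.106, about 11 points. With an assumed design effect of 2 for clustering it is 0.106 × √2 ≈ 0.15, about 15 points.

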Treatment of the DM and associated complications, dosing of the insulin, change from PO to insulin treatment and back to PO medications during hospitalization or at discharge will be guided by the admitting team with as needed help from the inpatient Endocrinology Consultation Service.

Decisions about insulin dosing or other medication use designed to treat hyper or hypoglycemia episodes or underlying diabetes mellitus will be made based on hospital POC blood glucose meters and not based on CGM readings alone.

Patients will be asked to give the research team “provider access” to their cloud CGM software, or to allow the team to download their CGM data prior to discharge if their reading devices do not automatically synchronize with the cloud software.

CGM data will be compared with POC blood glucose monitoring obtained in the hospital. Different patient variables (demographics, comorbidities, labs and vitals, administered medications) will be collected from electronic health record and will be evaluated to determine if they would interfere with CGM readings. The accuracy of CGM for glucose measurement in the hospital will be calculated.

Outcomes measured:

CGM accuracy when compared with POC monitors.

CGM accuracy at detection of hypo or hyperglycemia episodes when compared with POC monitors.

Number of CGM alarms and the clinical result of these alarms: nurse notification, treatment of hypo or hyperglycemia episodes, treatment for rapid declining glucose alarms.

Materials:

CGMs (sensors, transmitters and readers) belong to patients

Provider access to cloud CGM program will be granted to the research team by the patient.

Personnel:

A research assistant that will identify the patients and enroll them into the study.

Subject Information

Target accrual is the proposed total number of subjects to be included in this study at Mayo Clinic. A “Subject” may include medical records, images, or specimens generated at Mayo Clinic and/or received from external sources.

Target accrual: 150

Subject population (children, adults, groups): Admitted adult medical and surgical patients with Diabetes Mellitus type I or II that have their own CGM monitor present on admission or able to be placed after admission.

Inclusion Criteria:

Patients with Type 1 or 2 Diabetes Mellitus,

Patients 18 years of age or older,

Patients admitted under medical or surgical services.

Patients treated with diet alone, insulin (SQ, insulin pump) or oral hypoglycemic medications.

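### Apart from treatment after rapid-decline alarms, the alarm endpoint ignores whether alarms come before or after a glucose limit; with no comparator either, its counts cannot answer Aim 2 on prevention

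*Combined protocol and SAP*

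**What the plan says.** Under Research Question and Aims, the second aim is "To determine if alerts given by CGMs worn in the non-ICU hospital would prevent episodes of hyperglycemia and hypoglycemia". The hypothesis is stated more firmly: "acknowledgement by providers of high and low glucose trends will prevent episodes of hyper and hypoglycemia".

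The alarm endpoint appears in the same terms under Outcomes measured and under Endpoints (Secondary): "Number of CGM alarms and the clinical result of these alarms: nurse notification, treatment of hypo or hyperglycemia episodes". A further result closes the item: "treatment for rapid declining glucose alarms".

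The Methods describe which alerts start the pathway: "Patients alerted by their CGM about low glucose levels or fast downward or upward trending will be asked to notify their nursing staff". Then, "A POC blood glucose check will be done by nursing staff to confirm the alert or the trend". The research team obtains CGM data through cloud access, or patients are asked to "allow the team to download their CGM data prior to discharge".

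The Data Analysis Plan says that "Poisson or negative binomial regression will be utilized to assess count variables such as number of alarms, nurse notification, and hypo or hyperglycemia events", with adjustment for patient characteristics. The limits <70, >180 and >250 appear under Endpoints, where they define strata for MARD. Every enrolled patient wears a CGM, and no comparison group is named.

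**The concern.** An alert can prevent an episode only if it sounds before the episode begins. The endpoint records how many alarms sounded and what staff did next. Of the results it lists, treatment of an episode is by its nature a response to something that has already happened: more such treatments mean more treated episodes, not fewer episodes. A high count could be read as support for Aim 2 or as evidence against it, and the plan gives no rule for choosing.

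The Methods send two kinds of alert down one pathway: alerts for a level that is already low, and alerts for a fast trend that may still be in range. Total alarms and notifications pool the two. What is at stake is one of the study's two aims, since this is its only alarm endpoint.

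**Working it through.** The plan gives no figure for alarms, episodes or prevention, so there is nothing to reproduce. The check is a reading of the text, followed by two illustrations in which every alarm input is assumed.

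**1. What Aim 2 needs, against what the plan supplies**

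- *Alarm type:* partly supplied. Treatment after rapid-decline alarms is listed apart from treatment of episodes. Rising-trend alarms have no matching item, although the Methods include them in the notification pathway.
- *Position of the alarm relative to a limit:* not supplied. The three limits are used for MARD only. A rapid-decline alarm can itself sound before or after the low limit is crossed.
- *Link from alarm to later episode:* not supplied. There is no time window, no matching rule and no definition of a prevented episode. The count models relate totals to patient characteristics.
- *Chance of an episode had nobody responded:* not supplied, because there is no comparator.

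**2. Lead time**

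Lead time = (alarm level − limit) / rate of fall. With the plan's limit of 70, and with assumed alarm levels and rates of fall per minute:

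- alarm at 80, falling 1 per minute: (80 − 70)/1 = 10 minutes
- alarm at 80, falling 3 per minute: (80 − 70)/3 = 3.3 minutes
- trend alarm at 100, falling 2 per minute: (100 − 70)/2 = 15 minutes
- alarm at 70, any rate: (70 − 70)/rate = 0

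Lead time can therefore run from none to a quarter of an hour, depending on settings that the protocol does not give.

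**3. What the counts can say about prevention**

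Episodes prevented = A × f × (p0 − p1), where A is the number of alarms, f the share sounding before the limit is crossed, p0 the chance of crossing without a response, and p1 the chance with one. Assume A = 100, p0 between 0.2 and 0.8, and p1 between 0 and p0.

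- f unknown (0 to 1): the lowest value is 0; the highest is 100 × 1 × (0.8 − 0) = 80.
- f recorded as 0.5: the highest value is 100 × 0.5 × (0.2 − 0) = 10 at p0 = 0.2, and 100 × 0.5 × (0.8 − 0) = 40 at p0 = 0.8. The lowest is still 0.
- 30 treated rapid-decline alarms taken alone, all assumed to be before the limit, with p0 from 0 to 1: from 0 to 30 × (1 − 0) = 30.

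Recording the before/after split removes the uncertainty in f. It leaves p0 unknown, so the lower end stays at zero.

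**The case against.** The strongest objection is that timing is not the main obstacle. With a valid comparator, the planned models for episode counts could address prevention directly, without ordering a single alarm. Without one, no classification of alarms can. This stands. A reader might infer that the missing split is by itself why prevention cannot be shown, or that adding it would let Aim 2 be answered; the documents support neither.

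Second, the endpoint does list rapid-decline treatment separately, so it would be wrong to say that level and trend alarms are wholly pooled. That also stands, though the item covers falling trends only and is tied neither to a limit nor to an outcome.

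Third, timing summaries have their own bias. Lead times come only from episodes that occurred, which are failures of prevention. A pre-limit alarm with no crossing may be a prevented episode or a false alarm. This limits what the summaries can claim, but it does not make the pooled counts more informative.

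Fourth, the split could be derived later from the CGM trace and the confirmatory POC check. Perhaps so, but a rule chosen after the data are seen leaves the window and the classes open. The protocol promises CGM data without saying that alarm times are included, and it admits flash sensors scanned at intervals of up to 8 hours.

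**Conclusion.** The point holds in limited form. Following the plan as written gives counts of alarms, notifications and treatments that cannot answer a question about prevention, for two reasons together: alarms are not placed in time against a limit or a later episode, and no comparator is named. The conclusion rests on the text and not on any assumed number. The range of 0 to 80 prevented episodes per 100 alarms only illustrates how little the counts determine.

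A reader might also infer that most alarms come too late to prevent anything, since a low alarm set at 70 has no lead over a limit of 70. The documents do not support this. They give no alarm setting for patients' own devices, no rate of fall and no split between level and trend alarms, so the share of late alarms could be anything from 0 to 100%.

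This should be changed, but it does not threaten the study: the endpoint is secondary, and the primary endpoint, MARD, is unaffected.

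**What to change.** Add an alarm analysis to the Data Analysis Plan before any alarm data are examined:

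- Where the CGM download holds alarm times, classify each alarm as level or trend.
- Separately for <70, >180 and >250, record whether that limit was already crossed on the CGM trace when the alarm sounded. A single in-range/out-of-range split at 70–180 will not do, because an alarm that follows 180 may still precede 250.
- For each limit, report the share of episodes preceded by an alarm, the lead time, and the share of pre-limit alarms followed by a crossing within a fixed, pre-stated window.
- State beside these results that an alarm with no crossing may be a prevented episode or a false alarm, and that lead times describe only episodes that occurred.
- Word the Aim 2 conclusion as descriptive, about the opportunity for alerts to act before an episode, and not as prevention, unless a comparator is defined.
- Report devices without recoverable alarm times separately.

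The cost is some extra analysis work, an early check of which devices export alarm times, and fewer alarms counted in support of Aim 2. Defining a comparator would be a larger change to the design; the descriptive wording avoids the need for it.
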